Poststudy Anticancer Therapy Status																	X	X	X	X	

Study Period ^a	Screening		Indu	ctior	1 Pha	ise (C	Cycle	s)			Conso	lidati	on Ph	ase (C	ycles)		EOT	Po	sttreatr	nent	Notes
Treatment Cycles	Screening			(C1			C2			(C3			C4 to 18	C>18	DC	Safety FU	FU Visits	Survival FU	
Cycle Day	-28 to -1	1	8	15	22	29	36	1 to 36	1	8	15	22	29	36	1 to 36	1 to 36					
Study Week		1	2	3	4	5	6	7 to 12	13	14	15	16	17	18			DC	Days	Every 6 Weeks Post DC	Every	
Scheduled Window (days):		3	±3	±3	±3	±3	±3	±3	±3	±3	±3	±3	±3	±3	±3	±3	±3	±7	±7	±7	
Patient-reported Outcomes	•																				•

Study Period ^a	Screeningb		Indu	ction	Pha	ise (C	ycles	s)			Conso	lidati	on Ph	ase (C			EOT		sttreatn		Notes
Treatment Cycles	Screening			C	21			C2			(23			C4 to 18	C>18	DC	Safety FU	FU Visits	Survival FU	
Cycle Day	-28 to -1	1	8	15	22	29	36	1 to 36	1	8	15	22	29	36	1 to 36	1 to 36					
Study Week		1	2	3	4	5	6	7 to 12	13	14	15	16	17	18			DC	30 Days Post Last Dose	Every 6 Weeks Post DC	Every 12 Weeks	
Scheduled Window (days):		3	±3	±3	±3	±3	±3	±3	±3	±3	±3	±3	±3	±3	±3	±3	±3	±7	±7	±7	
Tumor Tissue Collection																					
Tumor Blocks or Slides	X																				To include PD-L1 and MSI analysis. Central PD-L1 result will be masked to the site. A repeat sample will be required if submitted sample is inadequate. The planned MSI sample should be obtained at screening but may be collected postrandomization if needed.
Laboratory Assessments	1	1	ı				1	1		ı							l	1	1	1	******
Pregnancy Test – Urine or Serum	X	Х			X			х	х			X			х	х	X	Xh			Will be performed on Day 1 and Day 22 of C2 -C18. See Section 8.3.6. WOCBP require a negative pregnancy test within either 24 hours (urine) or 72 hours (serum) before the first dose of study intervention and before each subsequent testing day as indicated.
FSH (in WONCBP only)	X																				

Study Period ^a	Screeningb		Indu	ction	n Pha	ise (C	ycle	s)			Conso	lidatio	n Pha	ise (C			EOT		sttreatr		Notes
Treatment Cycles	Screening			(C1			C2			(23			C4 to 18	C>18	DC	Safety FU	FU Visits	Survival FU	
Cycle Day	-28 to -1	1	8	15	22	29	36	1 to 36	1	8	15	22	29	36	1 to 36	1 to 36					
Study Week		1	2	3	4	5	6	7 to 12	13	14	15	16	17	18			DC	30 Days Post Last Dose	Every 6 Weeks Post DC	Every 12 Weeks	
Scheduled Window (days):		3	±3	±3	±3	±3	±3	±3	±3	±3	±3	±3	±3	±3	±3	±3	±3	±7	±7	±7	
PT/INR and aPTT ^f	X																				After baseline, PT/INR should be tested as needed for participants on warfarin-based anticoagulation therapy.

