 - e. 6-lead ECG is allowed per institutional standard. Induction Phase (CAPOX): ECG at Screening, C1D1, C1D22. C2D1, and C2D22. ECGs in the Induction Phase should be performed approximately 2 hours post lenvatinib dose. Consolidation Phase (CAPOX): C3D1 and C3D22, and starting from C5, an ECG should be performed every 2 cycles (12 weeks). For high-risk participants (as defined in Section 8.3.3), conduct ECG monitoring every cycle. If lenvatinib is discontinued, an ECG is only required at EOT and Safety Follow-up Visits.
 - f. Screening laboratory assessments (PT/INR and aPTT, CBC, chemistry, C-reactive protein and urine dipstick) MUST be performed within 10 days of C1D1 or on C1D1 as long as results are available prior to administration of study intervention. Results from the most recent laboratory tests must be used to assess participant eligibility. After C1, predose laboratory procedures can be conducted up to 72 hours prior to dosing.
 - g. Dipstick is preferred but urinalysis may be used if the use of urine dipstick is not feasible. If a urine dipstick is abnormal follow Section 6.6.3.5. If lenvatinib is discontinued, urine dipstick is only required at EOT visit.
 - h. Pregnancy testing is required at the Safety Follow-up visit and at the end of relevant systemic exposure

1.3.2 Initial Treatment Phase: Lenvatinib Plus Pembrolizumab Plus mFOLFOX6 (Safety Run-in [Part 1] and Main Study [Part 2])

Stu	udy Period ^a	Screening	In	ıduc	ction	ı Ph	ase	(Cy	cles)		C	onsol	idatio	n Pha	ase (C	ycles	s)	EOT	Po	sttreatme	nt	Notes
Trea	atment Cycles	Screening ^b			(C1		•	C2				C3		`	C4 to 18	C>18	DC	Safety FU		Survival FU	
(Cycle Day	-28 to -1	1	8	15	22	29	36	1 to 36	1	8	15	22	29	36	1 to 36	1 to 36					
St	tudy Week		1	2	3	4	5	6	7 to 13	14	15	16	17	18	19			DC	30 Days Post Last Dose	Every 6 Weeks Post DC	12	
	d Window (days):		3	±3	±3	±3	±3	±3	±3	±3	±3	±3	±3	±3	±3	±3	±3	±3	±7	±7	±7	
Administrative P		1																	1	ı		T
Informed Consent	t	X																				Section 8.1.1.1
Reconsent at the fradiographic recur	first indication of rrence/progression																					Assessed by the investigator before the next cycle starts
Inclusion/Exclusion		X																				
Participant Identif	fication Card	X	X																			Update at C1D1
Medical History Prior/Concomitan Treatment Randon	it Medication Review	X	X		X		X		х	X			х			X	х	X	х			At C2 will be assessed on Day 1, Day 15, and Day 29. Will be assessed on Day 1 and Day 22 of C4-C18. See Section 6.5

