Pregnancy Test – Urine or Serum	X	X		X		X		x	x			х			X	X	X	Xh			At C2 will be assessed on Day 1, Day 15, and Day 29. Will also be assessed on Day 1 and Day 22 of C4-C18. WOCBP require a negative pregnancy test within either 24 hours (urine) or 72 hours (serum) before the first dose of study intervention and before each subsequent testing day as indicated. See Section 8.3.6.
FSH (WONCBP only)	X																				After baseline, PT/INR
PT/INR and aPTT ^f	X																				should be tested as needed for participants on warfarin-based anticoagulation therapy.
CBC with Differential ^f	Х			X		X		X	X			X			X	X	X	X			At C2 will be assessed on Day 1, Day 15, and Day 29. Will also be assessed on Day 1 and Day 22 of C4-C18. Starting from C19 it will be assessed on Day 1 of every cycle.
Chemistry Panel ^f	X			X		X		Х	X		X	Х			Х	X	X	X			At C2 will be assessed at Day 1, Day 15, and Day 29. Will be assessed on Day 1 and Day 22 of every cycle from C4 onwards.
C-reactive protein ^f	X								X												Screening and Cycle 3 only

Study Period ^a	Screening	In	duc	tion	ı Ph	ase	(Cyc	eles)		C	onsoli	idatio	n Pha	ase (C		s)	EOT	Po	sttreatme	nt	Notes
Treatment Cycles	Screening ^b			(C1			C2			C	23			C4 to 18	C>18	DC	Safety FU	FU Visits	Survival FU	
Cycle Day	-28 to -1	1	8	15	22	29	36	1 to 36	1	8	15	22	29	36	1 to 36	1 to 36					
Study Week		1						7 to 13	14	15	16	17	18	19				30 Days Post Last Dose	Weeks Post DC		
Scheduled Window (days):		3	±3	±3	±3	±3	±3	±3	±3	±3	±3	±3	±3	±3	±3	±3	±3	±7	±7	±7	
Urine Dipstick (Urinalysis) ^{f. g}	Х			X		Х		X	X		X	X			X	X	X				At C2 will be assessed at Day 1, Day 15, and Day 29. After Cycle 3, urine dipstick testing for protein will be performed within 3 days before Day 1 and Day 22 of every cycle while participants are taking lenvatinib.
HIV, Hepatitis B and C screen	X																				Required at baseline only if mandated by local health authority or as clinically indicated (Appendix 7).
Thyroid function (T3, T4, and TSH)	X							X	X						Х	X	X	X			Should be performed on Day 1 of every Cycle. Free T3 and Free T4 are acceptable. Participants may be dosed while thyroid function tests are pending.

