				>9		30 Days			All procedures are to be
Visit Timing/	1°	2	3 to 9	(lenvatinib	At	After		Every	performed before
Cycle Number	1		3107	only)	DC	Last	Every	12	administration of study
				omy		Dose	12 weeks	weeks	intervention unless otherwise
Scheduling Window (days)	+3	±3	±3	±3		+7	±7	±14	indicated
									Urine dipstick testing for protein
									will be performed within 3 days
									before Day 1 of every cycle while
Urine dipstick (Urinalysis)	X	X	X	X	X	X			participants are taking lenvatinib.
									If lenvatinib is discontinued, urine
									dipstick is only required at EOT
									and Safety Follow-up Visits.
									Perform within 10 days before SC
									C1.
PT/INR and aPTT/PTT	X								Additional testing to be conducted
1 1/11/11 4114 411 11/1 11	11								as clinically indicated for
									participants taking anticoagulant
									therapy.
									*Thyroid function tests will be
									performed at C1 and then on Day
									1 at every cycle thereafter.
									-Perform within 10 days before SC
Themaid function (T2 T4 and									C1. After SC C1, collect within
Thyroid function (T3, T4, and TSH)	X*	X	X	X	X	X			3 days before dosingParticipants may be dosed in
1511)									subsequent cycles after SC C1
									while thyroid function tests are
									pending.
									-May use central laboratory only if
									local laboratory is not capable.
A.E. 1	1	 	.: 0.1166.1 . 1		1	. 	1 1 (CVDV)	1 1 1/2	W. D.C. 1

AE=adverse event; aPTT=activated partial thromboplastin time; β-HCG=beta-human chorionic gonadotropin; CBC=complete blood count; CXDY=Cycle X Day Y; DC=discontinuation; ECG=electrocardiogram; ECOG=Eastern Cooperative Oncology Group; EOT=end of treatment; FT4=free thyroxine; hr/H=hours; INR=international normalized ratio; PD=progressive disease; PT=prothrombin time; PTT=partial thromboplastin time; QXW=every X weeks; qd=once daily; QTc=corrected QT interval; SAE=serious adverse event; SC=Second Course; T3=triiodothyronine;

T4=thyroxine;; TSH=thyroid-stimulating hormone; UA=urine analysis; WOCBP=woman of childbearing potential.

Note: Second Course will be for eligible participants from Part 1 and Part 2.

a. If DC Visit occurs ≥30 days from last dose of study intervention, a Safety Follow-up Visit is not required.

c. C1D1 procedures should be completed within 28 days of radiographic BICR verified disease progression.

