Contraceptive use by women should be consistent with local regulations regarding the methods of contraception for those participating in clinical studies. If the contraception requirements in the local label for any of the study drugs is more stringent than the requirements above, the local label requirements should be followed.

Informed Consent

8. The participant (or legally acceptable representative) has provided documented informed consent/assent for the study.

Additional Categories

- 9. Has a performance status of 0 or 1 on the ECOG Performance Scale within 3 days prior to the first dose of study treatment.
- 10. Has provided a tumor tissue sample for PD-L1 and MSI biomarker analysis. If the initial tissue is inadequate for the analysis, an additional specimen will need to be provided.

- 11. Has adequately controlled BP with or without antihypertensive medications, defined as $BP \le 150/90$ mm Hg and no change in antihypertensive medications within 1 week prior to randomization.
- 12. Has adequate organ function as defined in the following table (Table 3). Specimens must be collected within 10 days prior to the start of study intervention.

Table 3 Adequate Organ Function Laboratory Values

System	Laboratory Value
Hematological	
Absolute neutrophil count (ANC)	≥1500 /mcL
Platelets	≥100,000 /mcL
Hemoglobin	≥9 g/dL or ≥5.6 mmol/L ^a
Renal	
Calculated ^b creatinine clearance	≥50 mL/min
Hepatic	
Total bilirubin	≤1.5 X ULN OR Direct bilirubin ≤ ULN for participants with total bilirubin levels >1.5 ULN
AST (SGOT) and ALT (SGPT)	≤2.5 X ULN OR ≤5 X ULN for participants with liver metastases
Albumin ^c	≥3.0 g/dL
Coagulation	
International Normalized Ratio (INR) or Prothrombin Time (PT) Activated Partial Thromboplastin Time (aPTT)	≤1.5 X ULN unless participant is receiving anticoagulant therapy as long as PT or PTT is within therapeutic range of intended use of anticoagulants ≤1.5 X ULN unless participant is receiving anticoagulant therapy as long as PT or PTT is within therapeutic range of intended use of anticoagulants

ALT (SGPT)=alanine aminotransferase (serum glutamic pyruvic transaminase); AST (SGOT)=aspartate aminotransferase (serum glutamic oxaloacetic transaminase); GFR=glomerular filtration rate; ULN=upper limit of normal.

$$\frac{\text{(140-age [years]} \times \text{weight [kg])}}{\text{Serum creatinine (mg/dL)} \times 72} (\times \text{ F})^*$$

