 - b. ALT or AST >3 × ULN and (TBL >2 × ULN or INR >1.5). Although Table 5 advises pembrolizumab to be withheld (interrupted), Table 8 and Table 9 advises lenvatinib to have no dose modification or a reduction, if this criterion is met, both drugs must be permanently discontinued immediately.

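### The INR limb of liver stopping rule 3b has no scheduled input after screening outside warfarin users, and the rule overlaps with the entry limits in Table 3

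*Combined protocol and SAP*

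**What the plan says.** **The rule.** Section 6.6.4.1, item 3b, applies to participants on lenvatinib plus pembrolizumab. Its condition is "ALT or AST >3 × ULN and (TBL >2 × ULN or INR >1.5" (the bracket closes after the INR term). The consequence is stated without exception: "if this criterion is met, both drugs must be permanently discontinued immediately". The item says that it takes precedence over the milder actions in Tables 5, 8 and 9. The INR term is an absolute value. It has no ULN multiple, no reference to baseline and no provision for anticoagulation.

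**The schedule.** In Section 1.3.1 (CAPOX) the PT/INR row has a screening entry only, with the note "After baseline, PT/INR should be tested as needed for participants on warfarin-based anticoagulation therapy". Section 1.3.2 (mFOLFOX6) carries the same note: "should be tested as needed for participants on warfarin-based anticoagulation therapy". The footnote on screening tests reads "Screening laboratory assessments (PT/INR and aPTT, CBC, chemistry, C-reactive protein and urine dipstick) MUST be performed within 10 days of C1D1" and also allows C1D1 itself. Second Course (Section 1.3.5) repeats PT/INR once before its first cycle. After that, the note "Additional testing to be conducted" ties further tests to clinical indication in participants taking an anticoagulant.

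**Liver monitoring.** Section 6.6.3.7 names ALT, AST and bilirubin as the liver tests, without INR. Total bilirubin is part of the required chemistry panel in Appendix 2, Table 24.

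**Eligibility.** Table 3 in Section 5.1 allows ALT and AST up to 2.5×ULN, or "≤5 X ULN for participants with liver metastases". For INR or PT the limit is "≤1.5 X ULN unless participant is receiving anticoagulant therapy as long as PT or PTT is within therapeutic range of intended use of anticoagulants".

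**The concern.** There are two separate problems.

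First, a mandatory and irreversible rule names an input that the schedule does not collect in most of the participants it governs. The only group for whom the initial-phase schedule foresees further INR tests is warfarin users, in whom a raised INR is the intended effect of a drug and says less about the liver. Whether the INR limb is assessed in anyone else depends on a site choosing to order the test.

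Second, the entry criteria and the stop rule use different limits for the same two analytes. A site that follows both literally can enrol a participant and find the permanent stop condition already met, with nothing having changed. Section 7.1 makes discontinuation from study intervention permanent, so sites that resolve the conflict differently would treat like participants differently, with no way back.

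**Working it through.** The plan gives no figure on this point, so the check sets the passages side by side and counts scheduled tests.

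**1. Scheduled inputs to item 3b through Cycle 18, Arm 1, after baseline.** Counts come from the chemistry rows and notes in Sections 1.3.1 and 1.3.2.

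- CAPOX: Cycle 1 Days 15, 22, 36 (3) + Cycle 2 Days 1, 22 (2) + Cycle 3 Days 1, 15, 22 (3) + Cycles 4 to 18 at two per cycle (15 × 2 = 30) = 38.
- mFOLFOX6: Cycle 1 Days 15, 29 (2) + Cycle 2 Days 1, 15, 29 (3) + Cycle 3 Days 1, 15, 22 (3) + 15 × 2 = 30, total 38.
- PT/INR in a participant not on warfarin: 0 with either backbone.

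So the transaminase term and the bilirubin limb can be evaluated at each of 38 panels, and the INR limb at none of them from scheduled data.

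**2. Does any other readable text order an INR when transaminases rise?** Section 6.6.3.7 does not list it. Table 24 lists PT/INR without a footnote linking it to liver tests. The potential-DILI criteria in Section 8.4.7 use ALT/AST, total bilirubin and alkaline phosphatase, not INR. The site guidance that section points to concerns participants who meet those criteria, which include raised bilirubin. Tables 8 and 9, to which Section 6.6.3.7 refers for liver injury, are redacted and cannot be checked.

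**3. Entry limits against item 3b.** The full rule needs ALT/AST above 3×ULN, plus INR above 1.5 or bilirubin above 2×ULN. Only the INR route is examined here.

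| Participant at entry | ALT/AST allowed | INR allowed | INR term can be met at entry | INR route of 3b can be met in full at entry |
|---|---|---|---|---|
| Anticoagulated, no liver metastases | ≤2.5×ULN | limit waived if in therapeutic range | yes | no |
| Anticoagulated, liver metastases | ≤5×ULN | limit waived if in therapeutic range | yes | yes, if ALT/AST is >3 to 5×ULN and INR >1.5 |
| Not anticoagulated, no liver metastases | ≤2.5×ULN | ≤1.5×ULN | depends on ULN | no |
| Not anticoagulated, liver metastases | ≤5×ULN | ≤1.5×ULN | depends on ULN | depends on ULN |

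**4. The ULN dependence.** The documents state no ULN for INR, so 1.0 to 1.2 is assumed. The entry limit is 1.5 × ULN:

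- ULN 1.0: 1.5 × 1.0 = 1.50, no gap above the absolute 1.5.
- ULN 1.1: 1.5 × 1.1 = 1.65, so an INR above 1.50 and up to 1.65 passes entry and meets the INR term.
- ULN 1.2: 1.5 × 1.2 = 1.80, so an INR above 1.50 and up to 1.80 does.

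**5. How the protocol treats abnormal baselines elsewhere.** The footnotes to Table 5 grade AST/ALT and bilirubin as multiples of baseline when baseline is abnormal. Item 3b, which overrides Table 5, has no such provision.

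**The case against.** The best case for the plan is that item 3b still works. Bilirubin, the other limb of an either/or condition, is measured at every panel. Section 8 and Appendix 2 allow additional tests whenever the investigator thinks them necessary, and Section 6.6.3.7 provides for liver tests on clinical indication. The redacted tables may call for coagulation tests. All of this stands. A reader might infer that the INR limb can never fire; the documents do not support that. They support only that it has no scheduled data in most participants.

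A reader might also infer that liver injury would go undetected. That does not follow either. The raised ALT has already been found by then. For immune-related elevations Table 5 prescribes action on pembrolizumab from Grade 2 and suggests liver tests weekly or more often. Item 3a covers sustained elevations above 5×ULN, and hepatic failure of any grade ends lenvatinib. What remains is possible delay, or variation between sites, in one trigger.

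On the overlap with eligibility, item 3 speaks of events that occur, within a section on attributing adverse events. One may read it as covering new findings only. That is a reasonable reading, but the text does not state it, and the consequence is immediate and irreversible.

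Finally, Section 9.9 says enrollment is complete, and as of Amendment 8 no new participants enter Second Course. Both limit the practical gain.

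**Conclusion.** The point holds in two parts.

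On measurement, the INR limb of item 3b has no scheduled input after screening in the initial treatment phase outside warfarin users (0 tests against 38 chemistry panels through Cycle 18), and no readable passage orders an INR when transaminases rise. The redaction of Tables 8 and 9 limits certainty on the second clause. Second Course is a partial exception, with one repeat before its first cycle.

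On consistency, Table 3 and item 3b conflict when both are followed literally, but only where three conditions coincide: liver metastases, ALT/AST above 3 and up to 5×ULN, and INR above 1.5. It would be too broad to say that eligible anticoagulated participants in general meet the rule at entry; without liver metastases the 2.5×ULN limit prevents it. Extension to participants not on an anticoagulant rests on the assumed laboratory ULN: there is no gap at 1.0, and at 1.2 the gap runs from above 1.50 to 1.80.

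The documents do not say how many participants fall in the overlap, so its frequency is unknown. A reader might infer that counts of discontinuation due to adverse events in Arm 1 are distorted. That is not supported: Appendix 3 excludes pre-existing conditions that do not worsen from the definition of an adverse event, so a stop on unchanged baseline values would not clearly be counted as one.

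**What to change.** Reconcile Sections 1.3.1, 1.3.2 and 1.3.5, Table 3 in Section 5.1, Section 6.6.3.7 and item 3b of Section 6.6.4.1 in two respects:

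- The schedule of activities and item 3b should agree, so that the input item 3b requires is available when the rule has to be applied.
- The documents should give one consistent instruction for participants who were eligible with a raised INR, with ALT/AST above 3×ULN, or with both. This includes stating whether INR is meant as an absolute value or as a multiple of ULN, since Table 3 and item 3b differ.

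The sponsor's medical team decides when an INR is taken, which limits apply and how such participants are managed. No threshold or testing rule is proposed here.

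The cost is protocol wording and, depending on that decision, occasional local coagulation tests. The benefit is limited to participants still on treatment and to any extension study that carries this text forward.

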6.6.4.2 Chemotherapy

[figure not shown]
The investigator may also attribute each toxicity event to the chemotherapy administered (capecitabine, oxaliplatin, and/or 5 FU). Dose modification should be performed taking the following criteria into consideration.

- Treatment for each new cycle may be delayed if the scheduled off-drug periods are not adequate to allow for recovery to the guideline for restarting each study treatment.
- If a dose reduction for toxicity occurs with any agent, the dose may not be re-escalated.
- Dose reduction of only one chemotherapy agent is appropriate if, in the opinion of the investigator, the toxicity is clearly related to one of the treatments. If, in the opinion of the investigator, the toxicity is related to a combination of 2 chemotherapy agents, the dose of both drugs may be reduced according to the recommended dose modifications. If the toxicity is considered related to the combination of 3 agents, chemotherapy may be considered to be reduced, interrupted or discontinued. Lenvatinib and/or pembrolizumab should be interrupted or discontinued according to the recommended dose modifications (Section 6.6.2 and Section 6.6.3, respectively).

PRODUCT: MK-7902 PROTOCOL/AMENDMENT NO.: 015-08

• If any adjustments to the chemotherapy dose modification guidelines are required per local guidelines, a Sponsor consultation is strongly recommended.

If toxicity is not otherwise specified, investigators should refer to the label or local guidelines for oxaliplatin, 5-FU, and capecitabine for dose adjustments.

MK-7902-015-08 FINAL PROTOCOL 10-JUN-2025

6.6.5 Chemotherapy Dose Modification

Dose delays and treatment restarts will be made at the discretion of the site investigator according to institutional guidelines or local standard practice. If any adjustments to the chemotherapy dose modification guidelines are required per local guidelines, a Sponsor consultation is strongly recommended. If a dose reduction for toxicity occurs with any agent, the dose may not be re-escalated.

In participants with unrecognized DPD deficiency, acute, life-threatening toxicity may occur when participants are treated with fluoropyrimidine. We recommend DPD testing as appropriate per local guidelines. Participants who require dose modification on Cycle 1 are not eligible for the study.

